Number and length of the project's in-person and phone sessions will not be matched between conditions. An important component of DO-MoST is its supportive nature, apart from specific content. It would be quite difficult to match time and attention DO-MoST and UC groups receive without also equating support. **UC.** All patients, regardless of condition, will receive usual inpatient care at the Palo Alto or Ann Arbor VA. At both sites, implementation of ORYX measures requires that, under usual care, when a patient screens positive on the AUDIT-C administered at intake, a provider (social worker, nurse) provides BI, i.e., tells the patient that problems are associated with alcohol use, and about recommended drinking limits; notes the patient as ready to change drinking or not, and as agreeing to treatment or not. If the patient agrees to treatment, specialty addiction services are notified. Both sites have addiction outpatient and residential specialty care offering behavioral therapies (the 4 targeted in this study), pharmacotherapy (the 3 targeted in this study), and 12-step meetings, and Patient Aligned Care Teams within primary care.

**DO-MoST.** Patients assigned to the DO-MoST condition will receive usual care plus the DO-MoST intervention. They will attend one 50-minute individual session during their inpatient stay with a Decision Coach (a trained clinical provider, e.g., MSW). Patients in DO-MoST will also attend 6 biweekly 15-minute telephone sessions from the same Decision Coach. In our current HSR&D project with detox inpatients, 100% of patients completing a baseline interview also participated in the inpatient session with the TeleCoach.

At the initial session, the Decision Coach and patient will engage in MI to discuss the patient's medical condition and need to make decisions about drinking goals, and their benefits and adverse effects, i.e., abstinence vs. moderation vs. no change. MI components include empathy when giving personalized feedback (Engage); conveying the patient's responsibility for change (Focus); and support of the patient's self-efficacy to make changes (Evoke, Plan). MI includes reviewing patients' values (e.g., good health and relationships) and substance use patterns and their consequences. The discrepancy between patients' substance use and ability

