**Help utilization.** We will use the TLFB to assess patients' use of VA and non-VA help for alcohol and drug use (type and amount of pharmacotherapies, behavioral treatments, mutual-help groups), including setting (inpatient, residential, outpatient, primary care, e.g., BIs). Primary outcomes for alcohol are any help use (yes/no for initiation) and duration of use (engagement). The primary outcome for engagement will be duration (not completion) of treatment because the duration and continuity of care are more closely related to outcomes than is treatment completion; and our operations partners stated that in light of adaptive treatments, treatment completion is not cut-and-dried among AUD patients, such that duration is more reliable and meaningful. In addition, recommendations (e.g., from NIH) are that help be obtained for at least 1-2 years when beginning recovery from AUD; such sustained help is needed to "retrain brains" affected by chronic alcohol use. We will also use the Addiction Severity Index (ASI) to assess the participant's VA and non-VA history of lifetime treatment use including addiction, mental health, and medical-surgical care (outpatient, inpatient, residential, emergency). Data on non-VA health services use will be collected at baseline and follow-ups to help determine whether the two condition arms are balanced and ensure that any observed changes in VHA services use are not due simply to changes in non-VA care.

Related functioning. We will use selected portions of the ASI to fill in information missing from the TLFB and Veterans SF-12. The ASI, used to monitor VHA addiction patients' outcomes systemwide and in our projects, is a structured, clinical research interview that assesses 4 problem areas in addition to substance use and medical status: psychiatric, family/social, legal, and employment. In each area, a composite score is produced from items that are standardized and summed to provide an internally consistent evaluation of patient status in the past 30 days. Scores range from 0 to 1, with higher scores indicating poorer outcomes.

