Research assistants, blinded to patients' condition assignment, will collect self-report data by telephone at 3 months, which will be upon completion of the intervention for the group in the DO-MoST condition, and then 6 and 12 months post-baseline. We will use an intent-to-treat design and so will follow patients who do not complete the intervention. Six months is a necessary follow-up point because most (60%-80%) patients treated for AUDs who relapse do so within this interval. Twelve months is a necessary follow-up point because the 6 months preceding that time point continue to be of high risk for relapse. Follow-up assessments will be conducted by telephone because patients may not reside in close geographical proximity to the Palo Alto or Ann Arbor VA. As noted (A.7), we have successfully used telephone interviews to collect follow-up data in HSR&D studies with inpatients. Follow-up interviews will take approximately one hour each. Patients will have the option of completing the interview in shorter sessions, with breaks, due to scheduling needs or fatigue.

We will measure patients' drinking and help preferences using the same measure with the Decision Coach at baseline. We will use the AUDIT-C, DSM 5 for alcohol diagnoses, TLFB, and SF-12 to measure substance use and medical status at follow-ups, supplemented by portions of the ASI. The TLFB (covering the period since the prior interview at each follow-up) will assess the same primary alcohol outcomes (abstinence, percent of drinking days, of heavy drinking days) and other substance use indices assessed at baseline. The ASI will provide recent (past 30 days) alcohol and drug use composite scores. The TLFB and ASI are valid and reliable when given by telephone. We will be able to compute dichotomous scores regarding abstinence from alcohol, drugs, and both alcohol and drugs over the assessed periods. The SF-12 will yield the primary outcome reflecting overall physical health status.

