The TLFB will also be used to measure self-reported VA and non-VA alcohol-related, mental health, and medical help (treatment types, amounts, and settings) since the previous interview. Primary outcomes will be any use of alcohol help, and duration (weeks) of help. The ASI's selected portions on functioning will produce psychiatric, family/social, legal, and employment composite scores, and assess housing status. We will use measures used at baseline to assess motivation to change alcohol use, commitment to abstinence, self-efficacy to resist drinking, and Decisional Conflict with regard to drinking help options at follow-ups.

B.3.9 Procedures to Locate and Follow Patients. To ensure high follow-up rates, we will adhere to well-established procedures for locating and following substance use disorder, psychiatry, and medical patients in longitudinal studies. We have extensive experience in retaining research participants using proactive retention strategies, tracking protocols, and interviewer training procedures. Our Centers have conducted long-term studies with extremely high follow-up rates, e.g., 80% among individuals with AUDs followed for 16 years, 80% among depressed patients and controls followed for 23 years; 92% for addiction patients at 1 year, and 84% for dual diagnosis patients at 2 years. Our retention strategies include (1) research assistant interviewers are comfortable with the population under study and trained to establish rapport, (2) maintain toll-free telephone numbers for participants to report contact information changes (especially useful for patients who may lose their ongoing access to a telephone during the study), (3) obtain and verify in-depth locator and tracking information at intake, and update records at each interview and between interviews, (4) maintain consistent contact between interviews (e.g., thank you cards to enhance rapport and verify addresses), (5) keep detailed records of every contact and contact attempt, and (6) use the internet for tracking (e.g., Department of Corrections websites). We will use these procedures to target follow-up rates of at least 70%.

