B.3.10 Measuring Use of VHA Health Care Services. We will collect data on participants' use of VHA health care, including services from behavioral health providers in primary care, and addiction, mental health, and medical-surgical services. These data will be used to address the hypothesis that patients in DO-MoST, compared to patients in UC, will be more likely to enter alcohol treatment and attend treatment for a longer duration, and have fewer and delayed (i.e., greater number of days until) acute care episodes (Aim 2, Hypotheses 1 and 3). The data source for VHA health care utilization will be the CDW for VHA-provided inpatient, residential, and outpatient care, pharmacy services, and primary care behavioral health. We will also search the Fee Basis files for all records for study participants.

To measure the utilization of VHA care, we will obtain all records for study participants for all health care encounters that occur in the one-year period prior to, and ending one year after, study enrollment (i.e., one year post-index hospitalization). Variables extracted from records of inpatient or residential care will include patient ID (SCRSSN), station, treating specialty (bedsection), date of service, diagnosis and procedure codes, and length of stay. Variables extracted from records of outpatient care will include patient ID, station, clinic stop code, date of service, diagnosis and procedure codes, and numbers of visits. Variables extracted from records of primary care encounters will include patient ID, station, date of service, and procedure codes indicating behavioral health care provision. We will classify VHA care as pertaining to addiction, psychiatry, or medical-surgical conditions based on stop code or treating specialty code. Fee Basis care will also be classified by setting and purpose of visit.

To assign hospital stays with multiple bedsections to a single category, we will classify inpatient stays to addiction if there is such a bedsection segment, to psychiatry if there is a psychiatry bedsection segment, and to medical-surgical otherwise. Outpatient care will be classified as addiction, psychiatry, or medical-surgical based on clinic stop codes. Emergency Department visits will be identified through clinic stop codes. Prescription drugs will be classified as AUD, medication-assisted treatment for opioid use disorder, psychiatry, or medical-surgical based on the VHA drug class.

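### Two data sources serve the primary help-use outcomes with no rule joining them, and the one named beside those outcomes is self-report that can differ by arm

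*Combined protocol and SAP*

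**What the plan says.** **Self-report.** Section B.3.6 (Help utilization) says "We will use the TLFB to assess patients' use of VA and non-VA help for alcohol and drug use" and names any help use and its duration as the primary help outcomes. Section B.3.8 repeats this for follow-up: "The TLFB will also be used to measure self-reported VA and non-VA alcohol-related, mental health, and medical help", and the next sentence is "Primary outcomes will be any use of alcohol help, and duration (weeks) of help". The TLFB is described as "covering the period since the prior interview at each follow-up". With interviews at 3, 6 and 12 months, the recall windows are about 3, 3 and 6 months.

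**Records.** Section B.3.8 opens by listing Corporate Data Warehouse (CDW) data as a follow-up source that covers treatment entry, type, timing and duration. Section B.3.10 adds Fee Basis files and extracts all VHA encounters up to one year after enrollment. It links these records to both entry into care and time spent in it: "These data will be used to address the hypothesis that patients in DO-MoST, compared to patients in UC, will be more likely to enter alcohol".

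**Blinding and contact.** "Research assistants, blinded to patients' condition assignment, will collect self-report data by telephone at 3 months", and again at 6 and 12 months. Section B.3.4 states "Number and length of the project's in-person and phone sessions will not be matched between conditions".

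**Follow-up.** Section B.3.9: "We will use these procedures to target follow-up rates of at least 70" percent.

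**Analysis.** Section B.3.11 models any alcohol help and its duration without naming a source.

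**The concern.** One primary outcome has two possible versions, and the plan does not choose between them. If self-report and records disagree, an analyst could settle the matter after seeing both results.

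The version placed next to the outcome definition is also the more exposed to bias. Under Section B.3.4, DO-MoST patients have six Coach calls over 12 weeks. The Coach works in a non-confrontational style but seeks commitment to obtaining help, and asks at each call about treatment and mutual-help. Usual-care patients have no such calls. When both groups are later interviewed, DO-MoST patients may recall help better, or be more inclined to report it. Blinding the interviewer does not remove an error that arises in the patient.

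The error could reach the mediation analysis in Section B.3.12. Help use is the mediator there, and the drinking outcomes come from the same interviews, so errors may be shared.

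**Working it through.** **The plan's own figure.** The documents give no figure for how help use is ascertained. The nearest is the sample size in B.3.1: 156 patients, 78 per arm, for an effect size of 0.50. Assuming 80% power and two-sided 0.05, n = 2(1.960 + 0.842)² / 0.50² = 63 per arm. Assuming 20% attrition, 63 / 0.80 = 79, close to 78. Other assumed combinations fit as well, so the inputs cannot be recovered. This figure neither supports nor weakens the point.

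**Patients without an interview.** At the B.3.9 floor of 70%, 0.30 × 156 = 46.8, or about 47 patients at a given wave. Their VHA records are extracted regardless.

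**Spurious difference.** Let p be true initiation, equal in both arms, and let fD and fU be the shares of non-users who report help in DO-MoST and usual care. Only non-users can over-report, so:

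spurious difference = (fD − fU) × (1 − p)

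The values of fD and fU are assumptions; no document gives them. Two rates quoted in A.4 illustrate p: 18% (attendance at a placement evaluation) and 43% (treatment entry in a pilot program).

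| fU | fD | p | Spurious difference |
|---|---|---|---|
| 5% | 5% | any | 0 |
| 2% | 15% | 18% | 0.13 × 0.82 = 10.7 points |
| 2% | 15% | 43% | 0.13 × 0.57 = 7.4 points |

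The 18% is a proxy. A.4 adds that half of those attending the evaluation started treatment. That would put p at 9% and the difference at 0.13 × 0.91 = 11.8 points.

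**Effect on a test.** Take no true effect, over-reporting in DO-MoST only, and a pooled two-sided z-test at 0.05, evaluated by exact binomial enumeration. The two sizes are 55 per arm (0.70 × 78 = 54.6) and 78 per arm.

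| Over-reporting in DO-MoST | p = 18% | p = 43% |
|---|---|---|
| 10%, 55 per arm | 0.18 | 0.09 |
| 10%, 78 per arm | 0.24 | 0.10 |

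Across the same values of p and n, the rejection rate is 0.06 to 0.10 at 5% over-reporting and 0.21 to 0.65 at 20%. The planned analysis is a mixed model over several waves, so these figures show the order of size only.

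**Passages side by side.** B.3.6 and B.3.8 put VA and non-VA help together under self-report. B.3.10 gives treatment entry and duration to the records. B.3.6 also says non-VA data help show that changes in VHA use are not simply shifts in non-VA care, which treats VHA use as a result in its own right. No section ranks, merges or reconciles the two.

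**The case against.** **H1 already uses records.** A reader might infer from B.3.8 that the help outcomes rest on recall alone. The documents do not support that, because B.3.10 assigns records to treatment entry and duration. What stands is that two sources serve one outcome without a rule.

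**Records do not hold the same information.** Help includes mutual-help and non-VA care, and the Decision Aid offers mutual-help as an option. VHA records cannot show mutual-help, and show non-VA care only through Fee Basis. B.3.10 also sorts encounters as addiction care, not alcohol care. This stands: the TLFB cannot simply be replaced.

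**The Coach does not press patients.** B.3.4 has the Coach explain that the aim is not to change the patient, and usual-care patients also get a brief intervention and a referral if they agree. This tempers the expected bias. It does not remove the six calls that ask about help in one arm only.

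**The sizes are soft.** The over-reporting rates are assumed and their range includes no bias. Subtracting 2% from 15% and reading off 13 points would hold only if nobody truly obtained help. Nor do 47 patients lack all self-report: 70% is a minimum for a wave, the prior trial in A.7 exceeded 80% at one year, there are three interviews, and the mixed model keeps patients with some waves missing.

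**The TLFB is validated.** General validity does not rule out error that differs by arm.

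**Conclusion.** The point holds as a gap in outcome definition with a plausible route to bias; it does not show that bias will occur. It rests firmly on three features of the plan: primary help outcomes placed under self-report, records assigned to the same hypothesis with no rule between them, and help-focused Coach calls in one arm only. That patients know their arm is inferred from the design, but it is hardly avoidable.

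The size rests on assumed over-reporting rates: zero if the arms over-report equally, and about 7 to 11 points at 2% against 15% with true initiation of 43% to 18%. At modest over-reporting (5% in DO-MoST only) the false-positive rate rises little. The sponsor should make the change, because a less bias-prone measure of VHA care is already being collected for every patient.

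**What to change.** 1. Define the VHA component of both H1 outcomes (addiction treatment entry, weeks of treatment, AUD prescriptions) from CDW and Fee Basis records for all randomized patients. List the stop codes, treating specialties and drug classes that count.
2. Use the TLFB only for mutual-help and for non-VA care that those records do not show.
3. State that records govern VHA care when the sources disagree.
4. Treat the self-report component as missing, not as no help, for patients not interviewed.
5. Report the records-only VHA comparison on all randomized patients as a prespecified sensitivity analysis beside the composite, and repeat the mediation analysis with the record-based measure.

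The H1 claim should not depend on the records-only result having the same sign. With no true effect that condition is met about half the time, so it protects little. It could also veto a real shift toward mutual-help.

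The cost is wording in the outcome definitions and analysis plan, plus the extra sensitivity runs; both data sources are already planned. The downside is that mutual-help and non-VA care still rest on self-report, and the records-only result understates total help.

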**B.3.12 Examine mechanisms (reasons DO-MoST is effective).** Alcohol help initiation and engagement will be examined as mediators between condition and outcomes. We will conduct a series of regression models (controlling for covariates, e.g., baseline value of the dependent variable) that correspond to a hypothesized causal sequence among (1) DO-MoST, (2) alcohol help utilization, and (3) better alcohol and medical outcomes. First, the dummy variable representing DO-MoST is the independent variable and the dependent variable is the outcome (e.g., abstinence, percent of heavy drinking days). In the second regression, DO-MoST is the independent variable and the dependent variable is the potential mediator (e.g., duration of alcohol outpatient help). In the third regression the potential mediator is the independent variable and the dependent variable is the outcome. If the coefficient for DO-MoST or potential mediator is significant in all cases, we will proceed. In the final regression, DO-MoST is entered simultaneously with the utilization variable as predictors of the outcome. If the coefficient for utilization is significant and the coefficient for DO-MoST on the outcome is reduced, then we will conclude that a mediating effect of utilization is supported, and evaluate whether the indirect effect of DO-MoST on the outcome via treatment is significant.

We will also determine if increases in treatment utilization associated with DO-MoST are mediated by the mechanisms of reduced decisional conflict and increased motivation, commitment, and self-efficacy. We will conduct a series of regression models that correspond to a hypothesized causal sequence among (1) DO-MoST (vs. UC), (2) the potential mechanisms, and (3) use of alcohol treatment, and control for covariates. Analyses will use the same general linear model approach described in the previous paragraph. We will conduct regression analyses (covariates controlled) to examine associations of DO-MoST dose (number of phone sessions completed) with patients' outcomes at follow-ups, using methods (e.g., instrumental variables) to account for possible problems associated with endogeneity. We will explore whether less intensive (e.g., 3-session) doses of DO-MoST are as effective as the full, 6-session dose.

Additional analyses will explore patients' baseline level of AUD (moderate or severe) as a moderator of condition-outcome associations; the needed interaction term (condition by diagnosis) will be added to the GLMM regressions. Results will indicate, for example, whether DO-MoST has a stronger association with patients' improved drinking when AUD symptoms are more severe. We will also examine patient age (e.g., <50, 50-64, >64 years old), race (e.g., white, not white), and homelessness as potential moderators; for

example, DO-MoST may be more effective when veteran patients are homeless. Although we will attempt to enroll every eligible female patient into the study, we are still unlikely to have enough women to conduct gender-related analyses. This will require examining DO-MoST at additional numbers of sites in subsequent studies to yield larger numbers of women who are medical-surgical inpatients with AUD.

**B.4 Aim 3: Process Evaluation of DO-MoST.** We will conduct a process evaluation to document critical factors at the system-, provider-, and patient-levels that affect the likelihood that DO-MoST could be implemented and sustained in VA, and the extent to which it needs to be adapted to be most effective with specific Veteran groups, such as patients with co-occurring mental health disorders (PTSD), women, and OEF/OIF/OND Veterans. We will use the RE-AIM Planning Tool to conduct semi-structured interviews with Key Informants, that is, providers of services to medical-surgical inpatients with AUDs, and patients with AUDs receiving medical-surgical inpatient care. The RE-AIM framework highlights information needed to evaluate an intervention's potential for implementation and widespread impact, including its *Reach* (how to reach the target population with DO-MoST: number, percent of target patients, and representativeness of patients who agree to DO-MoST), *Effectiveness* (how to know DO-MoST is effective: change in outcomes), *adoption* (organizational support: number, percent, and representativeness of target settings and providers who participate in implementation), *Implementation* (fidelity of DO-MoST's delivery; its time, costs), and *Maintenance* (sustainability). The RE-AIM Planning Tool asks questions of providers and patients within each framework domain regarding key issues that should be considered when planning implementation, for example: *Reach*: How to ensure that *all* medical-surgical inpatients with AUD accept DO-MoST; confidence that DO-MoST will attract all such inpatients despite mental health (PTSD), demographic (gender), and other factors. *Effectiveness*: Strengths of, and benefits anticipated from, DO-MoST; unintended negative consequences. *Adoption*: Greatest barriers to inpatient medical-surgical units adopting DO-MoST and systems for overcoming them; sources of potential staff resistance to DO-MOST; development of organizational support. *Implementation*: Ensure DO-MoST is delivered properly despite customization to facilities. *Maintenance*: Incorporate DO-MOST locally so that it is delivered over the long term, integrated into the regular practice of VA facilities. *Distribute ownership for implementing DO-MoST among inpatient medical-surgical, addiction, and other (primary care, social work, nursing) services.*

Interviews will help explain barriers to setting, provider, and patient participation in DO-MoST and how to address them; provider and patient perceptions about why DO-MoST is successful at achieving better outcomes; barriers to implementation of DO-MoST – site specific, and general -- and how to address them; and perceived value of, and how to sustain, DO-MoST in the absence of a funded project. They will also help plan if and how DO-MoST should be adjusted to appeal to and help subpopulations (female, OEF/OIF/OND).

The PIs will prepare a draft interview guide and finalize it with feedback from the project team (having had QUERI funding for similar evaluations) and pre-testing with 2 medical-surgical inpatient unit staff (physician, nurse). Recruitment and interview procedures for providers will be similar to those for Aim 1. Interviews will be conducted by the project's senior staff and research assistants who will be trained in carrying out such interviews (we have successfully conducted trainings before). We will interview 12 staff members at each of the 2 sites, including medical-surgical units' directors, other physicians, nurses, social workers, and administrators. Providers who participated in Aim 1 interviews will not be excluded from Aim 3 interviews because the Aims are related but do not overlap; the same staff members, such as unit directors, would provide crucial input for both Aims; and there will be a sizeable time gap between interviews. We will also interview addiction treatment providers within specialty and primary care teams at each site. Further, we will conduct interviews with 12 patients at each site; one-half will have received the intervention, and one-half will be in UC. Individuals cannot represent entire groups, but we will include Veterans from different groups based on mental health diagnosis, age, gender, and other factors. Interviews will be audiotaped when consent is given, conducted in person when possible and by phone otherwise, and last 30-60 minutes.

**B.4.1 Analysis Plan.** Using rapid analysis methodology, the PIs will listen to the interview transcripts and take detailed notes using the structure of the interview guide questions. We will focus on the components of the RE-AIM model to optimize the potential for implementation and sustainable adoption of DO-MoST across VA facilities, by creating tables regarding DO-MoST that will then be reviewed by the Co-Investigators. Tables will summarize and categorize barriers and facilitators by the patient, provider, and system levels and include potential solutions and potential-to-leverage columns that contain evidence-based implementation tools to be considered for more widespread usage of DO-MoST. Such factors will be used to inform interpretation of project findings and optimize subsequent implementation plans. In conjunction with the tables, we will develop a small set of key themes in each RE-AIM component that signify triangulated findings. We will identify factors facilitating and maintaining units' use of DO-MoST to reach medical-surgical inpatients with AUD and help
